3.6. Primary Objective

The primary objective of this study is to demonstrate that the all-cause mortality rate at 30 days post procedure is less than the pre-specified performance goal of 10.0%.

3.6.1. Primary Hypothesis

$$H_0: \pi \geq 10.0\%$$

$$H_a: \pi < 10.0\%$$

Where π denotes the binary rate of all-cause mortality rate at 30 days post procedure. This one-sided test will be carried out at the 0.05 significance level using the Fisher exact test.

3.6.2. Primary Endpoint Definition

The primary endpoint is the binary rate of all-cause mortality at 30 days post procedure. The numerator will be the number of subjects who died on or before 30 days post procedure, and the denominator will be the number of subjects in the safety set (defined in section Analysis Sets 3.4) who died on or before 30 days post procedure, or whose latest date of all follow-up visits, assessments, and events is at least 30 days post procedure.

In addition, the KM event rates for all-cause mortality at 30 days, 1 year, 2 years and 3 years, as well as the KM plot will be provided.

3.6.3. Rational for Choice of Hypothesis

The performance goal for all-cause mortality at 30 days was established through the following data sources:

- Data from the CoreValve IDE clinical study
- Review of the published literature on the Medtronic CoreValve System current through April 2013

Criteria for selection of the articles included the following:

- Study was published in peer reviewed journal
- Study was multi-center
- Results were representative of high or above risk population
- Results for all-cause mortality were reported by device type
- Study was not a first in man, feasibility, or confined to early Medtronic CoreValve experience

Of the literature reviewed, 4 articles were selected. Information on the historical data is presented in Table 1.

Table 1 Information on Control Data Sources for Primary Safety Endpoint

Author	Study Name	Number of CoreValve Patients	Age (years) Mean \pm SD	Logistic Euroscore (%) Mean \pm SD	STS Score (%) Mean \pm SD	All-Cause Mortality at 30 days (%)
US CoreValve IDE study: Extreme Risk Cohort ¹		639	83 \pm 8	23 \pm 17	10 \pm 6	9.1
US CoreValve IDE study: High Risk Cohort ¹		390	83 \pm 7	18 \pm 13	7 \pm 3	3.3
Bosmans	Belgian Registry	141	82 \pm 6	25 \pm 15	Not reported	11
Gilard	FRANCE 2 Registry	1043	82 \pm 7	21 \pm 14	14 \pm 11	9.4
Chieffo	PRAGMATIC	453	81 \pm 7	21 \pm 13	8 \pm 6	7.5
Moat	UK TAVI Registry	452	81 \pm 7	18 (11-28)	Not reported	5.8
Random effects meta-analytic rate						7.3
						(95% CI 5.4 - 10.0)

1. Data include all access routes.

The random effect meta-analysis showed that the all-cause mortality rate at 30 days post procedure for CoreValve was 7.3% with a 95% C.I. of 5.4% to 10.0%. We expect Evolut R TAV will have a similar rate as CoreValve, which is 7.3% at 30 days. And the all-cause mortality rate for Evolut R will not be higher than the upper bond of the 95% C.I. for CoreValve. Therefore the performance goal was set to 10.0%.

3.6.4. Sample Size Consideration

Assumptions for the sample size estimation are as followings:

One-sided alpha = 0.05

$\pi_0 = 10.0\%$

$\pi = 7.3\%$

Power = 90%

In the above expressions, π_0 and π denote the Performance Goal (null hypothesis proportion) and the expected true proportion, respectively, for all-cause mortality rate at 30 days. Using an exact binomial test, Power Analysis and Sample Size (PASS) software calculates that a total of 934 evaluable subjects is required to attain 90% power in a one-sided test at the 0.05 level of significance. The final sample size is increased to 1000 evaluable subjects to account for 7% attrition rate.

3.6.5. Data Collection and Analysis Methods

Death data will be collected on a separate site death case report form. All-cause death events will be adjudicated by the CEC. And the data on the CEC death adjudication form will be used in the analysis.

The all-cause mortality rate at 30 days post procedure will be compared with the performance goal of 10%, with a one-sided Fisher exact test at the 0.05 significance level. The analysis for this objective will be based on the safety set.

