2.7 Statistical Methods and Analysis

Any deviations from this section and/or the Statistical Analysis Plan will be described and justified in the Final Clinical Study Report, as appropriate.

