2.7.1 Primary Hypothesis

The primary endpoint of the study is the all-cause mortality at 30 days post procedure, which will be compared to a performance goal of 10.0%. Therefore the study hypotheses are:

$$H_0: \pi \geq 10.0\%$$

$$H_A: \pi < 10.0\%$$

Where π denotes the binary rate of all-cause mortality rate at 30 days post procedure. This one-sided test will be carried out at the 0.05 significance level using the exact test.

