This is a prospective, single arm, multi-center, observational, post market study. In Australia and Canada it is a prospective, single arm, multi-center pre-market study. Approximately 1000 subjects implanted with the Evolut R system will be included. Subjects will be followed at 30 days, 1, 2 and 3 years after the procedure. Based on clinical assessments during the course of the study, follow up may be extended to up to 5 years post procedure.

Enrollment parameters are included in the study to avoid introduction of bias to the trial results due to disproportionate enrollment. Enrollment shall not exceed 7.5% (75 patients) of the total implanted patients at any individual site. In addition, enrollment shall not exceed 40% (400 patients) of the total implanted patients at any individual country.

Enrollment will be competitive across sites. The per-site and per-country enrollment cap may be increased upon Sponsor approval. There is no set minimum number of patients to be enrolled per site; however there is an expected minimum enrollment of 15 subjects per site.

At the time when the study-wide enrollment cap of 1000 implanted subjects has been reached, further enrollment into the study will cease regardless of whether individual sites have reached their per-site cap.

The study methods include the following measures to minimize potential sources of bias:

- An external, independent Clinical Events Committee (CEC) will review and adjudicate, at minimum, all deaths and safety endpoint related adverse events. Safety endpoint results will be based on CEC adjudications.
- All sites will follow a standardized protocol for acquisition of echocardiographic endpoint data.
- An Echo Core Lab will evaluate all echocardiograms. Echocardiographic study endpoint results will be based on Core Lab assessments.
- Study sites should follow their institutional procedures for maintenance of echocardiography and laboratory equipment used for assessing the study variables.
- Study monitors will verify patients' data and ensure compliance with the Clinical Investigational Plan and other study requirements.

Subject selection criteria are based on the Instructions for Use of the Evolut R System.

Inclusion Criteria

- Symptomatic native aortic valve stenosis or a stenosed, insufficient, or combined surgical bioprosthetic valve failure necessitating valve replacement

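### The SAP names Fisher's exact test for a single-arm rate against a fixed 10.0% goal; that test needs a second sample the plan does not define, and the exact binomial test used for sizing was probably meant

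*SAP*

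**What the plan says.** SAP 3.6.1 sets H0: π ≥ 10.0% against Ha: π < 10.0% and continues: "This one-sided test will be carried out at the 0.05 significance level using the Fisher exact test". SAP 3.6.5 repeats the choice: the rate is "compared with the performance goal of 10%, with a one-sided Fisher exact test at the 0.05 significance level", in the safety set.

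The rest of the plan describes a one-sample problem:

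- **Design (SAP 2):** "This is a prospective, single arm, multi-center, observational, post market study".
- **Endpoint (SAP 3.6.2):** "The primary endpoint is the binary rate of all-cause mortality at 30 days post procedure", with one numerator and one denominator, defined on the safety set.
- **Comparator (SAP 3.6 and 3.6.1):** the constant 10.0%.
- **Sizing (SAP 3.6.4, and the same in Protocol 2.7.3):** "Using an exact binomial test, Power Analysis and Sample Size (PASS) software calculates that a total of 934 evaluable subjects is required".
- **Protocol 2.7.1:** "This one-sided test will be carried out at the 0.05 significance level using the exact test", without saying which exact test.

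**The concern.** Fisher's test conditions on the margins of a 2x2 table, so it needs an event count and a size for each of two groups. The plan supplies one group and a constant. The historical cohorts in SAP Table 1 do not fill the gap. They are used only to derive the goal, and their pooled rate is 7.3%, not 10%.

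The SAP therefore sizes the study on one test and names another for the analysis. Read literally, it leaves the analyst to make up a comparator sample or to run a test other than the one named. This is the only confirmatory hypothesis, since every secondary objective in SAP 3.7 is declared descriptive. Protocol 2.7 adds: "Any deviations from this section and/or the Statistical Analysis Plan will be described and justified in the Final Clinical Study Report", qualified there as applying where appropriate. A naming error left in place could thus need explaining for the primary endpoint. It would also leave the choice of test to be settled after the data are seen if the result falls near the boundary.

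**Working it through.** **Inputs from the documents** (SAP 3.6.4, Protocol 2.7.3): one-sided alpha 0.05, π0 = 0.10, true rate π = 0.073, power 90%, 934 evaluable subjects, final size 1000.

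**Step 1. Reproduce the plan's figure with the one-sample exact binomial test.** The cut-off c is the largest integer with P(X ≤ c | n, 0.10) ≤ 0.05. Power is P(X ≤ c | n, 0.073).

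| n | c (deaths) | exact alpha | power | p-value at c + 1 |
|---|---|---|---|---|
| 933 | 77 | 0.0396 | 0.880 | – |
| 934 | 78 | 0.0493 | 0.901 | 0.062 |
| 1000 | 84 | 0.0485 | 0.917 | 0.061 |

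The smallest n that reaches 90% power is 934, exactly as stated. The one-sample normal approximation gives 937.8, or 938, so the stated figure comes from the exact binomial calculation.

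**Step 2. Try Fisher.** For x deaths among n, against e deaths among m comparators, the one-sided p-value is P(H ≤ x). Here H is hypergeometric: n draws from n + m subjects, of whom x + e died. Neither e nor m is in the plan. Every comparator below is an assumption with about 10% deaths, and 3118 is the sum of the Table 1 cohorts (639 + 390 + 141 + 1043 + 453 + 452). Alpha and power hold the comparator fixed and take true rates of 10% and 7.3%. All rows are at n = 934.

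| Assumed comparator | c (deaths) | alpha | power |
|---|---|---|---|
| 93/934 | 71 | 0.007 | 0.667 |
| 94/934 | 72 | 0.009 | 0.711 |
| 312/3118 | 76 | 0.030 | 0.852 |
| 1,000/10,000 | 77 | 0.039 | 0.878 |
| 100,000/1,000,000 | 78 | 0.049 | 0.901 |

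The last row equals the binomial rule. A very large comparator with 10% deaths acts as the constant 10%.

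**Step 3. Where could the verdict differ?** In these cases, only at 72 to 78 deaths of 934. The expected count at 7.3% is 0.073 × 934 ≈ 68, and a result of 68 passes under every row. The count varies, however. With a true rate of 7.3%, the probability of 72 to 78 deaths is 0.9009 − 0.6672 = 0.234. That is how often the 93/934 illustration would fail where the binomial test succeeds. As an example at n = 1000, 80 deaths gives p = 0.018 by the binomial test and p = 0.069 by Fisher against 100/1000.

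**The case against.** The strongest reply is that the documents settle the matter themselves. The hypothesis in SAP 3.6.1 is a one-sample hypothesis, SAP 3.6.4 names the exact binomial test, and Protocol 2.7.1 and 2.7.3 are consistent with it. Only one exact test fits, and a competent statistician would run it. Doing so would not depart from the protocol at all, only from a label in the SAP, and one sentence in the report would cover it. The Fisher power figures come from invented comparators and should not be read as a power risk.

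Most of this stands. The mislabel reading is the likely one, any deviation would be from the SAP's wording rather than from the protocol's method, and the Fisher table shows only that the answer depends on an undefined input. What remains is that the wrong name appears in both places where the SAP specifies the primary test, and the test so named cannot be carried out. An inference from the sizing section is a weaker pre-specification than the correct name.

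**Conclusion.** The concern holds and should be fixed; confidence is high. The plan names a two-sample test for a one-sample comparison and defines no second sample. That a mislabel explains it is an inference, well supported by the exact match to 934.

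The practical size is small. The sizing is sound under the test evidently intended, and none of the Fisher cases run inflates alpha: all are conservative or equal to the binomial rule. The defect is in pre-specification of the only confirmatory test, with the pass mark open to dispute at 72 to 78 deaths of 934 under the comparators assumed here. It does not imply an expected loss of power.

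**What to change.** In SAP 3.6.1 and 3.6.5, replace the reference to Fisher with: *one-sided one-sample exact binomial test of H0: π ≥ 10.0% at the 0.05 level*. This is two phrases in the SAP, best changed before analysis. It needs no protocol amendment, no new data and no patients.

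Two additions are optional:

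- Report the matching Clopper-Pearson one-sided 95% upper bound, which agrees with the test at the boundary: 9.99% at 78/934 and 10.11% at 79/934.
- Name the test in Protocol 2.7.1 when the protocol is next amended for other reasons.

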3.6.6. Missing Data

Every effort will be undertaken to minimize missing data. A minimal amount of missing data is anticipated for the primary endpoint. However, if outcome data are missing, the primary analysis will be based on the complete case. To assess the potential impact of these missing data, a sensitivity analysis will be conducted which will include a complete case, a best case (assume missing subjects

are alive), a worst-case (assume missing subjects have died), and a tipping point analysis. In addition, the Kaplan-Meier rate at 30 days and its standard error, as a secondary analysis, will be used in the calculation of the test statistic.

3.7. Secondary Objectives

3.7.1. Secondary Objective #1 (Efficacy) - Device Success

This objective is to characterize the device success rate per the VARC-2 definition.

3.7.1.1. Hypothesis and/or Parameters to Be Estimated

The objective is descriptive and no statistical hypothesis test will be performed. The binary rate of device success and the two-sided 95% confidence interval will be estimated.

3.7.1.2. Sample Size Consideration

There was no sample size calculation for this objective.

3.7.1.3. Endpoint Definition

Device success, defined in accordance with the VARC-2 composite endpoint of device success:

- Absence of procedural mortality, and
- Correct positioning of a single prosthetic heart valve into the proper anatomical location, and
- Intended performance of the prosthetic heart valve, defined as the absence of patient-prosthesis-mismatch and mean aortic valve gradient less than 20 mmHg (or peak velocity < 3 m/sec), and absence of moderate or severe prosthetic valve regurgitation.

3.7.1.4. Data Collection and Analysis Methods

The components of device success will be determined as follows:

- No death event occurs within 30 days post-procedure, or on or before the discharge date (if the discharge date is longer than 30 days post-procedure);
- In the implant CRF, the answer to “Was a single Evolut R deployed in the proper anatomical location?” should be “YES”;
- The criteria for ECHO will be based on the ECHO Core Lab Data for the time interval “Discharge”:
 - Absence of patient-prosthesis-mismatch
 - For subjects with BMI < 30 kg/m², index effective orifice area (EOAi) > 0.85 cm²/m²
 - For subjects with BMI ≥ 30 kg/m², index effective orifice area (EOAi) > 0.70 cm²/m²
 - BMI = weight(kg)/(height (m))², where weight and height are recorded on the ECHO CORE LAB form
 - Mean aortic gradient < 20 mmHg or peak velocity < 3 m/sec;
 - Absence of moderate or severe prosthetic valve regurgitation. Total Aortic Prosthetic Regurgitation on the ECHO CORE LAB form not equal to moderate or severe.

All of the above components must be satisfied to count as a device success. If any of the above components fails, the endpoint will be counted as a failure.

For the overall device success rate, the numerator will be the number of subjects whose procedures result in device success as described above, and the denominator will be the number of subjects whose device success results are not missing (either success or failure). Note that this analysis excludes those subjects with a missing response to any of the above five components (eg, the field “Post-implant Severity of Total Aortic Regurgitation”=“Unable to Assess” or “Not Recorded”, missing mean aortic gradient, or missing peak velocity, etc.) and without a “NO” response to any

of the components. In addition to the device success rate, the 95% C.I. will also be provided. This objective will be analyzed for the implanted analysis set defined in section 3.4.

3.7.2.Secondary Objective #2 (Efficacy) - Hemodynamic Performance

This objective is to characterize the hemodynamic performance at 24 hours to 7 days (discharge) and 1 year post procedure.

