5.4.4 Subject Disposition

The Investigation site will maintain a log of all subjects enrolled in the clinical study, assigning an identification code linked to their names, alternative subject identification or contact information.

There are several scenarios in which a subject may exit the trial. Table 5 below details how the data will be handled for each scenario.

Table 5. Trial Exit Scenarios

Scenario	Follow-up Required	e-CRFs Required
Subject enrolled, but no implant attempted (i.e. not taken to the procedure room for implantation)	None	
 ▪ Inclusion/Exclusion e-CRF ▪ Baseline e-CRF (as applicable) ▪ AE e-CRF (as applicable) ▪ Trial Exit e-CRF
Subject enrolled, implant attempted (i.e. taken to the procedure room), but the subject does not receive the Evolut R TAV	30 days post-attempted implant for safety only	
 ▪ Inclusion/Exclusion e-CRF ▪ Baseline e-CRF (including TTE) ▪ Implant e-CRF ▪ Discharge e-CRF ▪ 30 Day e-CRF ▪ AE e-CRF (as applicable) ▪ Trial Exit e-CRF
Subject enrolled, implanted with Evolut R TAV, and has his/her valve explanted	Discharge following explant hospitalization or 30 days post implant (whichever comes later).	
 ▪ All required e-CRFs through last visit completed ▪ Surgical Reintervention e-CRF ▪ AE e-CRF (as applicable) ▪ Trial Exit e-CRF
Subject enrolled, implanted with Evolut R TAV, and exits the trial early due to any of the following: 
 ▪ Lost to Follow-up ▪ Death ▪ Withdrawal 	Through point of death, withdrawal, or last visit completed	
 ▪ All required e-CRFs through last visit completed ▪ AE e-CRF (as applicable) ▪ Trial Exit e-CRF
Subject enrolled, implanted and completes the trial requirements	Through 3 year follow-up	
 ▪ All required e-CRFs ▪ AE e-CRF (as appropriate) ▪ Trial Exit e-CRF

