Prosthetic valve thrombosis	Any thrombus attached to or near an implanted valve that occludes part of the blood flow path, interferes with valve function, or is sufficiently large to warrant treatment. *Valve-associated thrombus identified at autopsy in a patient whose cause of death was not valve related should not be reported as valve thrombosis.
Valve migration	After initial correct positioning, any observed movement (upward or downward) of the Evolut R within the aortic annulus from its initial position, with or without consequences.
Valve embolization	The Evolut R moves during or after deployment such that it loses contact within the aortic annulus
Ectopic valve deployment	Permanent deployment of the Evolut R in a location other than the aortic root
TAV in TAV deployment	Additional valve prosthesis is implanted within a previously implanted Evolut R because of sub-optimal device position and/or function, during or after the index procedure.
Hemolysis	Red cell destruction as evidenced by plasma free hemoglobin >50 mg/dl Minor hemolysis: No intervention required Major hemolysis: Requires intervention (e.g. iron supplements, transfusion, invasive intervention).
Frame fracture	Visual evidence on radiography or at explant of loss of contact between elements (cells) of the stent. Minor frame fracture: Does not require intervention, or is not associated with prosthetic valve dysfunction. Major frame fracture: Intervention required (e.g. reoperation, catheter re-intervention) or is associated with prosthetic valve dysfunction

PROSTHETIC VALVE ENDOCARDITIS

Any of the following:

1) Fulfillment of the following Duke criteria⁴⁷ for definite endocarditis:

- Histologic and/or microbiologic evidence of infection at surgery or autopsy, or
- 2 major criteria, or
- 1 major criteria or 3 minor criteria, or
- 5 minor criteria

Major and minor criteria are as follows:

Major Criteria:

- Blood cultures positive for Infective Endocarditis (IE)
 - Typical microorganisms consistent with IE isolated from two separate blood cultures, as noted below
 - Viridans streptococci, *Streptococcus bovis*, *Staphylococcus aureus*, or HACEK group
 - Community-acquired enterococci in the presence of a primary focus
 - Microorganisms consistent with IE isolated from persistently positive blood cultures defined as:
 - At least two positive cultures or blood samples obtained >12 hours apart, or

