3.7.2.4. Data Collection and Analysis Methods

Echo core lab data will be used. This objective will be analyzed for the implanted analysis set.

3.7.3.Secondary Objective #3 and #4 (Safety) - Event Rate of the VARC-2 Combined Safety Endpoint and Individual Safety Components at 30 Days

These two objectives are to characterize the safety event rates at 30 days based on the VARC-2 Combined Safety Endpoint and individual safety components.

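### The device success rule never reads the reintervention forms, so a subject whose Evolut R is replaced, explanted or given a second valve before the Discharge echo can count as a success or drop out as missing

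*SAP*

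**What the plan says.** Protocol 2.2.2 and SAP 3.7.1.3 define device success as no procedural death, one prosthetic valve in the right place, and valve performance as intended (no mismatch, acceptable gradient or velocity, no moderate or severe regurgitation).

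SAP 3.7.1.4 turns this into five data checks:

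- Survival: "No death event occurs within 30 days post-procedure", or by discharge if that is later.
- Single valve, correct position: the implant form must answer YES to "Was a single Evolut R deployed in the proper anatomical location".
- Mismatch, gradient or velocity, and regurgitation: "The criteria for ECHO will be based on the ECHO Core Lab Data for the time interval" Discharge.

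The combination rule is "All of the above components must be satisfied to count as a device success"; any failed check is a failure. For gaps it says "Note that this analysis excludes those subjects with a missing response to any of the above five components", as long as no check has failed.

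The protocol foresees late second valves. Appendix E.2 defines TAV in TAV as "Additional valve prosthesis is implanted within a previously implanted Evolut R because of sub-optimal device position and/or function, during or after the index procedure". The note on repeat procedures in Appendix E.1 sends them to separate surgical or catheter forms. SAP 3.7.3.4 counts such procedures on the Evolut R in the 30-day safety endpoint. After an explant, Protocol 5.4.4 (Table 5) keeps the subject in follow-up until "Discharge following explant hospitalization or 30 days post implant (whichever comes later").

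For hemodynamics, SAP 3.7.2.4 says only: "Echo core lab data will be used. This objective will be analyzed for the implanted analysis set".

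**The concern.** The single-valve check comes from a form about the index procedure, while the performance checks come from an echo taken later. Nothing requires the valve on that echo to be the Evolut R that was first implanted, and nothing links the echo date to a reintervention date. Protocol 5.2.1 (Table 3) and 5.2.4 only recommend 24 hours to 7 days for this echo, so a reintervention can come first.

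If it does, the echo describes a different prosthesis, or two prostheses, and a good result is credited to the index Evolut R. The same subject can then appear in one report both as a valve dysfunction needing a repeat procedure and as a device success. If the echo is missing, the subject leaves the denominator. Both routes raise the reported rate. Documenting device performance is the study objective, so the direction of the error matters even if the number of subjects is small.

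**Working it through.** The documents give no figure for this objective (SAP 3.7.1.2 states that no sample size was calculated), so there is none to reproduce. The check has two parts: run the SAP 3.7.1.4 rule on the possible cases, then show how much each misclassified subject moves the rate.

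**1. The rule applied.** Any failed check gives failure; otherwise any missing check gives exclusion; otherwise success. The first four rows concern a second valve or explant after the index procedure, with the implant form at YES.

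| Case | Result under SAP 3.7.1.4 | Reason |
|---|---|---|
| Echo after the reintervention, all echo checks pass, subject survives | Success | All five checks pass |
| Echo after the reintervention, an echo check fails | Failure | Echo |
| No Discharge echo, or not assessable, subject survives | Excluded | Missing |
| Death in the mortality window | Failure | Death |
| Second valve during the index procedure, form answered NO | Failure | Implant form |

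In none of the first four rows does the reintervention decide the result.

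**2. Size for subjects wrongly scored as successes.** With N assessed subjects, of whom m were replaced and then passed, overstatement = m / N. The documents give no m. Assumed shares of 0.5%, 1% and 2% with N = 1000:

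- 5 / 1000 = 0.5 points
- 10 / 1000 = 1.0 point
- 20 / 1000 = 2.0 points

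**3. Size for subjects excluded as missing.** Suppose the report shows S = 850 successes among N = 1000 (an assumed 85%) and k replaced subjects were dropped. Counting them as failures gives S / (N + k):

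- k = 5: 850 / 1005 = 84.6%, a fall of 0.4 points
- k = 10: 850 / 1010 = 84.2%, a fall of 0.8 points
- k = 20: 850 / 1020 = 83.3%, a fall of 1.7 points

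**4. Comparison with sampling error.** The exact (Clopper-Pearson) 95% interval half-width for N = 1000 is about 2.7, 2.3 and 1.4 points at assumed success rates of 75%, 85% and 95%. At 85%, even the 2% assumption stays inside the half-width; at 95% it exceeds it. Unlike sampling error, this shift always goes one way and does not shrink with a larger sample.

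**5. Hemodynamic summaries.** The implanted set is fixed when the valve is released (SAP 3.4), so a subject given a second valve by catheter stays in, and later echoes show the added valve. A subject with an early explant exits under Table 5 and has no 1-year echo. SAP 3.3 promises the number analysed, but no count of subjects with a second prosthesis or explant.

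**The case against.** A reader might infer that every subject replaced before the echo is counted as a success. The documents do not support that. Success also needs survival, an implant answer left at YES, and a complete, passing echo taken after the replacement. If the one scheduled echo comes first and shows the leak or gradient, the subject already fails.

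The implant form is not among the documents, and Protocol 6.1.1 tells sites to keep e-CRFs up to date, so a site might change the answer. That possibility stands, but it is not a cure. Repeat procedures have their own forms, and YES remains a true answer about a correct index deployment. Nothing tells the site to alter it.

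One can also argue that single-valve deployment is a procedure-level item and that the 24-hour-to-7-day window concerns only the echo. Even so, the performance checks would still be read from another prosthesis.

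A reader might assume that the discharge echo of an explanted subject is in the data. Table 5 asks for required forms through the last completed visit; it does not say that a surgical valve is imaged for the core lab under the Discharge interval. Exclusion as missing is equally consistent with the text.

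Nor does the failed valve vanish from the report: SAP 3.7.3.4 counts it in the 30-day composite and as a separate component, and Protocol 5.7.2 (Table 7) makes these events reportable. That keeps the event visible but does not correct the success rate.

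**Conclusion.** The concern holds in a limited form. Under SAP 3.7.1.4 a second prosthesis or explant between the index procedure and the Discharge echo can end as a success or an exclusion, and is never itself a failure. This conflicts with the single-valve, intended-performance definition and biases the rate in the device's favour.

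The size is unknown. It is 1 point for each 1% of assessed subjects wrongly scored as successes, and somewhat less for each 1% excluded. The 0.5% to 2% range is an assumption, not evidence of a material bias. The endpoint is descriptive, and the primary mortality test is untouched.

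For hemodynamics, a reader might conclude that only echoes before any replacement should be used. That is a debatable choice, and it would still leave the failed valve out of the 1-year summary. What the documents support is a need to report how many subjects are affected.

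**What to change.** Add to SAP 3.7.1.4: a catheter or surgical reintervention form recording a second prosthesis, or explant of the Evolut R, dated on or before the qualifying Discharge echo counts as failure of the single-valve component. If there is no such echo, the same applies to a reintervention dated within the Discharge interval. Because the protocol's echo window is only a recommendation, the sentence should also state which dates that interval covers.

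Add to SAP 3.7.2.4: beside each hemodynamic summary, show the number of subjects with a second prosthesis or explant before that echo. No change to which echoes are summarised is needed.

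The cost is SAP wording and a merge with reintervention data already read for SAP 3.7.3.4; no new data are collected. The reported device success rate may be slightly lower.
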